9.4.1 General Approach

Unless otherwise noted in the SAP, continuous variables will be summarized using the following descriptive statistics: n (non-missing sample size), mean, standard deviation, median, maximum and minimum. The frequency and percentages (based on the non-missing sample size) of observed levels will be reported for all categorical measures.

9.4.2 Analysis of the Primary Endpoint(s)

Descriptive summaries of immunogenicity data will be presented for the mITT population. If there are protocol deviations which may affect the analysis, a per-protocol (PP) analysis may also be performed.

Geometric Mean Titers (GMT) and Geometric Mean Fold Rise (GMFR) from baseline of SARS-CoV-2 specific antibody binding and neutralization titers will be calculated, along with 95% CIs, for all groups, at each timepoint. Summaries will also be displayed graphically. Geometric Mean Ratio (GMR_{D614G}) is defined as the ratio of a variant of concern to D614G (i.e Beta to D614G) will also be reported for all groups, at each timepoint, along with 95% CIs.

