^g Inability (e.g., failure of venipuncture) to collect all baseline samples on Day 1 will not exclude the subject from further participation in this study as long as a minimum of baseline blood volume is collected (refer to the MOP for the protocol defined minimum number of required aliquots). Blood volume for PBMC varies depending on the type of tubes used for blood collection (refer to the MOP).

^h Selected sites will perform PBMC separation on selected subjects (refer to MOP for more guidance).

ⁱ Blood volumes for early termination visit are not included in the blood volume totals.

^j After vaccination on Day 1, immunosuppressant drugs, COVID-19 related prophylaxis and therapies as well as vaccines will be recorded. For any SAE occurring at any time during the study, all medications will be recorded.

^k If an unscheduled visit is performed to evaluate an adverse event, vital signs and targeted physical exam will be performed, as indicated. If, in the judgement of the site investigator, the event, occurring within 4 weeks after vaccination, is a case of suspected myocarditis and/or pericarditis, the site will coordinate an appropriate diagnostic workup to make a determination of probable or confirmed myocarditis and/or pericarditis which may include, but is not limited to, an ECG, cardiac troponin testing and referral to a cardiologist (directly, or through the emergency department or primary care clinic). The suspected myocarditis and/or pericarditis case should be reported to the DMID Medical Monitor within 24 hours of site awareness.

^l Serum for biomarker testing will be collected on Day 4 and stored for potential biomarker testing at a central laboratory and compared to testing of an aliquot from serum obtained on Day 1. If an unscheduled visit is related to a concern for myocarditis and/or pericarditis within 4 weeks after vaccination, a 4 mL SST will be collected and stored for potential biomarker testing at a central laboratory.

^m If a participant is planning to receive a COVID-19 booster outside the study, an unscheduled visit will be performed where safety and immunogenicity (collection of sera, plasma and PBMC) assessments will be performed. However, if that planned visit falls within twice the window for an upcoming visit (e.g +/- 14 days for

D 91, +/-28 days for D 181 and D 271, +/- 56 days for D 366) then it will occur and be documented as out of window for the planned upcoming scheduled visit (refer to MOP for more guidance).

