^mIf a participant is planning to receive a COVID-19 booster outside the study, an unscheduled visit will be performed where safety and immunogenicity (collection of sera, plasma and PBMC) assessments will be performed. However, if that planned visit falls within twice the window for an upcoming visit (e.g +/- 14 days for D 147, +/-28 days for D 237 and D 327, +/- 56 days for D 422) then it will occur and be documented as out of window for the planned upcoming scheduled visit (refer to MOP for more guidance).

Note Windows for subsequent visits should be based off the preceding vaccination visit.

If intercurrent SARS- CoV-2 infection occurs between the first and prior to the planned second study dose or if a COVID-19 vaccine is given outside the study between the first and prior to the planned second study dose, no second vaccination will be given. Participants who do not receive a second dose will revert to the schedule of activities for single dose participants.

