the S protein variant common in o BA.4 and BA.5 lineages of the Omicron variant of SARS-CoV-2. Roll-out of a different bivalent vaccine, Prototype + Omicron BA.1 for use as a booster dose, will occur in other countries including the United Kingdom and Canada.^{49,50} We do know from this study and others conducted by the companies that antibody levels to various variants can be significantly increased by a fourth booster dose. Also based on the current study and studies conducted by the companies, a Prototype + Omicron BA.1 bivalent booster does increase the overall levels of antibody to various variants. However, there are no data to determine if one of these bivalent variant vaccines will provide better protection against symptomatic disease and a more robust immune response. Knowing that the highest risk of severe disease is still seen in the older population and to minimize the risk for participants in arms 16 and 17 (stage 4) we will limit enrollment to individuals between the ages of 18 to 49 years.

There may be benefit to society resulting from insights gained from participation in this study due to the emerging threat of the SARS-CoV-2 variants.

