4.2 Scientific Rationale for Study Design

An open-label study will facilitate the need for rapid review and dissemination of study data for public health reasons. Safety findings are not expected to be dissimilar from Phase 1/2/3 studies conducted for similar vaccine constructs. Randomization will improve comparisons between the different arms. Each stage will contain an arm with the prototype vaccine with the exception of stage 4.

Selected arms will assess 2 study doses of vaccine candidates to assess if 2 doses provide a more durable response and more specific to variant viruses.

We chose the interval of 4 months since a recent study performed by our investigators showed that an interval of 3 months between primary series and boost had acceptable safety and immunogenicity responses.¹⁹

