9. STATISTICAL CONSIDERATIONS

9.1 Statistical Hypotheses

This is a phase 2, open-label, multi-site clinical trial that is not designed to test a specific hypothesis. Rather, it is intended to obtain preliminary estimates in adults of the safety and immunogenicity of additional booster doses of SARS-CoV-2 variant vaccines.

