9.2.2 Sample Size Calculation for the Immunogenicity Endpoints

The primary objective of this study is to evaluate the magnitude and durability of SARS-CoV-2 specific antibody titers in serum samples. This objective is descriptive in nature and will be accomplished by estimating 95% confidence intervals (CI) for the geometric mean titer (GMT) at each timepoint when samples are collected.

The precision with which the GMT can be estimated from observed data depends on the standard deviation (SD) of the measurements, on the logarithmic scale, and the sample size. [Table 6](#) displays two-sided 95% confidence intervals for the GMT for several values of the observed antibody titer. [Table 6](#) also shows results assuming up to 10% attrition.

Table 6: Two-sided 95% confidence intervals based on observing a particular average \log_e -antibody titer in subjects' vaccine groups and potential strata sizes

Observed average \log_e antibody titer	SD of \log_e antibody titer	95% confidence interval of GMT in vaccine groups and strata			
		N = 100	N = 50	N = 25	N = 15
$\log_e(5)$	0.5	(4.5, 5.5)	(4.3, 5.8)	(4.1, 6.1)	(3.8, 6.6)
$\log_e(20)$		(18.1, 22.1)	(17.4, 23.1)	(16.3, 24.6)	(15.2, 26.4)
$\log_e(50)$		(45.3, 55.2)	(43.4, 57.6)	(40.7, 61.5)	(37.9, 66)
$\log_e(100)$		(90.6, 110.4)	(86.8, 115.3)	(81.4, 122.9)	(75.8, 131.9)
$\log_e(250)$		(226.4, 276.1)	(216.9, 288.2)	(203.4, 307.3)	(189.5, 329.8)
$\log_e(500)$		(452.8, 552.1)	(433.8, 576.3)	(406.8, 614.6)	(379.1, 659.5)
$\log_e(1000)$		(905.6, 1104.3)	(867.5, 1152.7)	(813.5, 1229.2)	(758.1, 1319)
$\log_e(5)$	1.0	(4.1, 6.1)	(3.8, 6.6)	(3.3, 7.6)	(2.9, 8.7)

Observed average \log_e antibody titer	SD of \log_e antibody titer	95% confidence interval of GMT in vaccine groups and strata			
		N = 100	N = 50	N = 25	N = 15
\log_e (20)		(16.4, 24.4)	(15.1, 26.6)	(13.2, 30.2)	(11.5, 34.8)
\log_e (50)		(41, 61)	(37.6, 66.4)	(33.1, 75.6)	(28.7, 87)
\log_e (100)		(82, 121.9)	(75.3, 132.9)	(66.2, 151.1)	(57.5, 174)
\log_e (250)		(205, 304.9)	(188.2, 332.2)	(165.5, 377.8)	(143.7, 435)
\log_e (500)		(410, 609.7)	(376.3, 664.3)	(330.9, 755.5)	(287.4, 869.9)
\log_e (1000)		(820, 1219.5)	(752.6, 1328.7)	(661.8, 1511)	(574.8, 1739.8)

* Assumes approximately 10% attrition.

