9.4 Statistical Analyses

Interim analyses of safety and immunologic response data will be done, as needed.

The final analysis will be performed after the final data lock and clinical study report (CSR) completed when all primary safety endpoint data and all secondary immunogenicity endpoint data are available and received by the SDCC. Any available data from the exploratory immunogenicity endpoints may also be included in the CSR. Remaining exploratory immunogenicity endpoint data may be included in an addendum to the CSR, publication of manuscript(s), or other report(s). Abbreviated analysis plans that describe planned analyses to facilitate dissemination of study data for public health reasons, including manuscript publication(s), will be developed by the SDCC as needed. A full statistical analysis plan (SAP) will be developed by the SDCC and finalized prior to the primary data lock.

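### Should Section 9.4.2 have named a between-arm GMT ratio, given that the trial is randomised?

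*Protocol*

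**What the plan says.** Section 9.4.2 provides that GMTs and GMFRs from baseline of "SARS-CoV-2 specific antibody binding and neutralization titers will be calculated, along with 95% CIs, for all groups, at each timepoint". It then adds a geometric mean ratio of a variant of concern to D614G. That ratio compares two viruses in the same participants, not two vaccines.

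On purpose, Section 9.1 states that the trial is not built around a hypothesis: "it is intended to obtain preliminary estimates in adults of the safety and immunogenicity of additional booster doses". Section 9.2.2 says of the primary objective: "This objective is descriptive in nature and will be accomplished by estimating 95% confidence intervals (CI) for the geometric mean titer (GMT") at each sampling time. Section 9.4.6 rules out formal hypothesis tests in the interim analyses.

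On design, Section 4.2 says: "Randomization will improve comparisons between the different arms. Each stage will contain an arm with the prototype vaccine with the exception of stage 4". Section 6.3.2 sets equal allocation within each stage, and Section 4.1 stratifies by age and confirmed prior infection. Section 2.2.2 reports "no data to determine if one of these bivalent variant vaccines will provide better protection against symptomatic disease and a more robust immune response", and Stage 4 randomises between those two bivalent vaccines.

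On further analysis documents, Section 9.4 announces a full SAP before the primary data lock. It also says: "Abbreviated analysis plans that describe planned analyses to facilitate dissemination of study data for public health reasons", including manuscripts, will be developed as needed.

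**The concern.** Per-arm titres with CIs could be produced without randomising anyone. What randomisation adds is the contrast, and Section 4.2 says as much. Yet neither Section 9.4.2 nor the rest of Section 9 names an estimate of variant against prototype, or of arm 17 against arm 16 in Stage 4. The data for one are in hand: Day 1 serum is drawn, the mITT population in Section 9.3 requires a pre-vaccination sample, and the strata are recorded at enrolment.

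Two losses would be at stake. Readers might judge differences by whether separate CIs overlap, which is too strict. And precision from the Day 1 titre and the strata would go unused. Arms 2 and 3 also receive the same vaccine on Day 1 and differ only from Day 57, but no pooled summary is named for the visits before that.

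**Working it through.** **Inputs.** Log_e SD 0.5 and 1.0, two-sided 95% CIs and about 10% attrition (Section 9.2.2, Table 6). Arms of 100 in Stages 1 and 4 and of 50 in Stages 2 and 3 (Table 1). The correlation r between Day 1 and later log titre is not in the protocol, so 0.3, 0.5 and 0.7 are assumed.

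**1. The plan's own figure.** One-group CI = GMT × exp(± t(0.975, n−1) × SD/√n). At GMT 1000 and SD 1.0:
- n = 100: exp(1.984 × 0.1) gives 1219.5, as printed in Table 6.
- n = 50: exp(2.010 × 0.1414) gives 1328.7, as printed.

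These cells reproduce at the full column N.

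**2. Can the unadjusted ratio be had from the planned outputs?** Yes. Take a per-arm result like the Table 6 cell for n = 100, SD 1.0. The log half-width is ln(1219.5/1000) = 0.198, so SE = 0.198/1.984 = 0.100. For two such arms:
- SE of the log ratio = √(0.100² + 0.100²) = 0.1414.
- CI factor = exp(1.972 × 0.1414) = 1.322.

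The same steps for 50 v 50 give exp(1.984 × 0.200) = 1.487. At SD 0.5 the factors are 1.150 and 1.220. With 10% attrition they are 1.158 and 1.342 (90 v 90), and 1.233 and 1.520 (45 v 45), at SD 0.5 and 1.0. Only per-arm GMT, CI and n are needed. The same steps applied to GMFR give a contrast already corrected for baseline.

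**3. What adjustment would add.** With equal SDs, relative variances are 1 for the GMT contrast, 2(1−r) for the GMFR contrast and 1−r² for the adjusted contrast. The fair comparison is with the better of the first two.

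| r (assumed) | GMFR | Adjusted | Adjusted / better simple | Log CI narrower by | CI factor, SD 1.0, 100 v 100 |
|---|---|---|---|---|---|
| 0.3 | 1.40 | 0.91 | 0.91 | 5% | 1.322 to 1.305 |
| 0.5 | 1.00 | 0.75 | 0.75 | 13% | 1.322 to 1.273 |
| 0.7 | 0.60 | 0.51 | 0.85 | 8% | 1.241 to 1.220 |

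The further gain from the strata was not computed.

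**4. Pooling arms 2 and 3 at Days 15 and 29.** 200 v 100 at SD 1.0: exp(1.968 × √(1/200 + 1/100)) = exp(0.241) = 1.273, against 1.322 for one arm. The log half-width falls from 0.279 to 0.241, about 14%. This needs no correlation and can be computed from the two per-arm results. It concerns one vaccine at two visits.

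**5. Does the protocol contradict itself?** Section 9.1 asks for preliminary estimates, Section 9.2.2 for CIs around GMTs, and Section 9.4.2 delivers them. Section 4.2 is design rationale: concurrently randomised, stratified arms make the per-arm estimates comparable, whoever forms the ratio. The remark in Section 2.2.2 is risk and benefit background, not an analysis objective. Nothing in Section 9.4.2 says its outputs are the only ones, and Section 9.4.6.2 separately allows immunogenicity analyses by vaccine arm.

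**The case for a change.** The best case for the concern runs as follows. Descriptive does not mean single-group: a ratio with a CI and no test fits Section 9.1. At SD 1.0, non-overlap of separate CIs needs an observed GMT ratio of about 1.49 (n = 100) or 1.77 (n = 50), while a direct ratio CI excludes 1 at 1.32 or 1.49. The trial is open label, results may be released while it runs, the abbreviated plans are written only as needed, and the SAP is due only before the primary data lock. Naming the contrast and covariates in the protocol would fix them before anyone sees results.

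The arithmetic stands, and so does the remark that a ratio would be informative. What does not follow is that the plan is at fault.

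- Judging by overlap is a reader's error, which the published per-arm figures allow a reader to avoid.
- The model for an adjusted contrast belongs in the SAP or an abbreviated plan. The SAP is not at hand and may contain it.
- The adjusted ratio would not be out of reach even if the study never produced it. Section 10.1.4.2 says de-identified individual data, the SAP and the code will be made available after publication, though on request and with approval, and Section 10.1.9.5 leaves sharing to the investigator's discretion.
- For arm 3 after its second dose, a contrast with prototype limited to those who received that dose would set a post-randomisation subset against a whole arm, because Section 7.1.3 withholds the dose for infection, outside vaccination and other events. The two-dose question in Section 4.2 is arm 3 against arm 2, which a list of variant-to-prototype ratios does not address.

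**Conclusion.** The concern does not hold. Section 9.4.2 names valid outputs that match the descriptive objective in Sections 9.1 and 9.2.2. It contradicts nothing and leads to no wrong conclusion. A between-arm ratio would be an addition beside unchanged outputs, of a kind commonly specified in the SAP.

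In size, the unadjusted contrast is already recoverable. Adjustment for Day 1 titre would narrow the log CI by roughly 5% to 13% over the assumed range of r, given equal SDs. The one gain that needs no assumed correlation, about 14% from pooling arms 2 and 3, is confined to Days 15 and 29 and can also be computed from per-arm results. This conclusion rests on the list in Section 9.4.2 being non-exclusive, as its wording allows, and on further analysis detail being left to the documents promised in Section 9.4.

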6.3.2 Randomization and Blinding

Subjects will be randomized to study intervention in an equal allocation ratio for each stage. The study will be open label and study sites will administer product to a subject according to which study arm the subject has been assigned. Sites will be asked to recruit for all arms within a stage.

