9.2 Sample Size Determination

9.2.1 Sample Size Calculation for the Safety Endpoint

Rare AEs are not demonstrable in a clinical study of this size; however, the probabilities of observing one or more AEs given various true event rates are presented in [Table 5](#). With the assumption that all enrolled subjects will likely complete immunizations and safety visits in this relatively short duration study, the following statistical considerations apply. With approximately 100 subjects in each arm there is a greater than 99.9% chance of observing at least one AE of probability 10%. With approximately 50 subjects in each of the strata subgroups (or arms), there is a 99.5% chance of observing at least one AE of probability 10%. With approximately 25 subjects in each of the strata subgroup combinations (assuming equal numbers and 100 per arm), there is a 92.8% chance of observing at least one AE of probability 10%. Finally, with approximately 15 subjects in the smallest of the strata subgroup combinations (assuming unequal numbers and 100 per arm or 50 per arm), there is a 79.4% chance of observing at least one AE of probability 10%. Therefore, if no AEs of a given type occur in a group (or strata), we can be relatively confident that they will occur in fewer than 10% of people if the vaccine is implemented.

Table 5: Probability of Observing one or more Adverse Event for Various Event Rates in one vaccine group (or strata).

N	“True” Event Rate	Probability of Observing \geq 1 events (%)	N	“True” Event Rate	Probability of Observing \geq 1 events (%)
100	0.1%	9.5	50	0.1%	4.9
	0.5%	39.4		0.5%	22.2
	1.0%	63.4		1.0%	39.5
	2.0%	86.7		2.0%	63.6
	3.0%	95.2		3.0%	78.2
	4.0%	98.3		4.0%	87
	5.0%	99.4		5.0%	92.3
	10.0%	>99.9		10.0%	99.5
	15.0%	>99.9		15.0%	>99.9
	20.0%	>99.9		20.0%	>99.9
	30.0%	>99.9		30.0%	>99.9

N	“True” Event Rate	Probability of Observing ≥ 1 events (%)	N	“True” Event Rate	Probability of Observing ≥ 1 events (%)
25	0.1%	2.5	15	0.1%	1.5
	0.5%	11.8		0.5%	7.2
	1.0%	22.2		1.0%	14
	2.0%	39.7		2.0%	26.1
	3.0%	53.3		3.0%	36.7
	4.0%	64.0		4.0%	45.8
	5.0%	72.3		5.0%	53.7
	10.0%	92.8		10.0%	79.4
	15.0%	98.3		15.0%	91.3
	20.0%	99.6		20.0%	96.5
	30.0%	>99.9		30.0%	99.5

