9.4.6.2 Interim Immunogenicity Review

Interim data review of immunogenicity will be performed as often as needed to inform public health decisions.

Statistical analyses of immunogenicity endpoints, by vaccine arm, may be performed when subjects have completed key immunogenicity visits. Immunogenicity reviews may be shared with the DSMB, as determined by DMID.

Data may be disseminated to public health officials and partners as needed and included in publications and presentations to inform the global scientific community.

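### Arms 2 and 3 are the same Beta + Omicron intervention through Day 29, but no combined dose-1 estimate is planned, so each reported estimate has the precision of 100 subjects when 200 are available (minor, optional improvement)

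*Protocol*

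**What the plan says.** - **Arms.** In Protocol 1.1, Table 1, arms 2 and 3 are both Stage 1, Moderna platform, Beta + Omicron, 100 subjects, first dose on D1. Arm 2 has no second dose; arm 3 has one at D57.
- **Allocation.** Section 6.3.2: "Subjects will be randomized to study intervention in an equal allocation ratio for each stage". The two arms are therefore randomised against each other at 1:1 within Stage 1.
- **Reason for the second dose.** Section 4.2: "Selected arms will assess 2 study doses of vaccine candidates to assess if 2 doses provide a more durable response". That question starts at D57.
- **Visits.** Tables 2 and 3 in section 1.2 share D1, D4, D8, D15 and D29, with the same windows. Serum for serology is drawn at D1, D15 and D29 in both.
- **Titer summaries.** Section 9.4.2: GMT and GMFR "will be calculated, along with 95% CIs, for all groups, at each timepoint". The term for the groups is not defined there.
- **Interim titers.** Section 9.4.6.2: "Statistical analyses of immunogenicity endpoints, by vaccine arm, may be performed when subjects have completed key immunogenicity visits".
- **Other output.** Section 9.4.6 allows primary endpoint results to be released during the study, aggregated by study arm. Section 9.4.6.1 has the DSMB see adverse event reports arm by arm. Section 9.4.4 names the safety population but no grouping for its adverse event summaries.
- **Planning.** Section 9.2.1 works from "With approximately 100 subjects in each arm", and Tables 5 and 6 stop at N = 100. Section 9.1 says the trial "is not designed to test a specific hypothesis".

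**The concern.** Until D57 the protocol has one intervention under two labels. Subjects are randomised concurrently, given the same product on the same day, and seen at the same visits through D29. Wherever the protocol states a grouping by name it is by arm, and nowhere does it plan a dose-1 estimate that uses both arms.

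In a trial whose purpose is estimation, precision is the main statistical yield. Two estimates for one product each carry a wider interval than the data allow. They will also differ by chance, and nothing says which one represents the product after one dose. This matters most for early releases: D15 and D29 are the first post-dose titers, and by-arm results may be published before the full SAP has to be final, which section 9.4 sets at the primary data lock.

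**Working it through.** **Inputs.** N = 100 per arm (Table 1; section 9.2.1), so 200 combined. SD of the log_e titer 0.5 or 1.0 (Table 6). The planned summary is "estimating 95% confidence intervals (CI) for the geometric mean titer (GMT) at each timepoint" (section 9.2.2). Adverse event rates are those of Table 5.

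**1. Reproduce Table 6.** CI = GMT × exp(± t(0.975, n−1) × SD / √n). At n = 100, t = 1.984.

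- SD 1.0: half-width 1.984 × 1.0 / 10 = 0.1984, factor 1.219, so GMT 100 gives 82.0 to 121.9.
- SD 0.5: half-width 0.0992, factor 1.104, so GMT 100 gives 90.6 to 110.4.

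Both match Table 6.

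**2. Combine the arms.** At n = 200, t = 1.972 and √200 = 14.142.

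- SD 1.0: half-width 1.972 / 14.142 = 0.1394, factor 1.150.
- SD 0.5: half-width 0.0697, factor 1.072.

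| SD | One arm, n = 100 | Arms 2 + 3, n = 200 |
|---|---|---|
| 1.0 | 82.0 to 121.9 | 87.0 to 115.0 |
| 0.5 | 90.6 to 110.4 | 93.3 to 107.2 |

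The ratio of half-widths is 0.1394 / 0.1984 = 0.70, about 30% narrower on the log scale at either SD.

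**3. Attrition.** The Table 6 footnote reads "Assumes approximately 10% attrition", but the N = 100 column reproduces with n = 100, not 90 (what the footnote marks may have been lost in text extraction). With 10% loss, 90 against 180, SD 1.0 and GMT 100, the intervals are 81.1 to 123.3 and 86.3 to 115.8. The ratio is again 0.70.

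**4. Reproduce Table 5, then combine.** P(at least one event) = 1 − (1 − p)^n.

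| True rate | n = 100 (as in Table 5) | n = 200 |
|---|---|---|
| 0.1% | 9.5% | 18.1% |
| 0.5% | 39.4% | 63.3% |
| 1% | 63.4% | 86.6% |
| 2% | 86.7% | 98.2% |

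For a solicited reaction seen in half the subjects (an illustrative rate), the exact 95% CI narrows from 20.3 to 14.3 percentage points.

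**5. Chance difference between the two arms.** The 95% range for the ratio of two GMTs with the same true value is exp(± 1.972 × SD × √(2/100)). The upper factor is 1.32 at SD 1.0 and 1.15 at SD 0.5.

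**6. How far the arms stay comparable.** Section 8.3.5 collects unsolicited events until 28 days after each vaccination, which is Day 29 for dose 1. After D29 arm 2 is next seen at D91 (Table 2). Arm 3 is seen at D57, and Table 3 marks unsolicited events at ten visits, consistent with D57 being one of them. Ascertainment is therefore alike through Day 29 but not between Day 29 and Day 57.

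**The case against.** The strongest reply is that reporting randomised arms as randomised is a sound default, and that adding a combined column is a table-level choice for the SAP. Much of this stands.

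- A reader might infer that the protocol allows only separate summaries. It does not say so. Section 9.4.2 does not define its groups or exclude a combined one, and section 9.4.6.2 is permissive.
- A reader might infer that half the subjects are discarded. They are not. All 200 are reported, each estimate is unbiased with a valid interval, and the log-scale means could be combined later from the published GMTs, intervals and counts.
- A reader might infer that reactogenicity is also fixed by arm. Section 9.4.4 states no such grouping; for safety the by-arm wording is in sections 9.4.6 and 9.4.6.1.
- No stated target is missed. The trial is descriptive, section 9.2.1 accepts that rare events are out of reach, and its 10% benchmark event is already seen with more than 99.9% probability at n = 100.
- Showing the separate arms beside a combined one still leaves their chance difference visible.

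The SAP argument answers only part of the point. By-arm release is written into the protocol and may come before the full SAP is final. The abbreviated analysis plans in section 9.4 could add a combined group, but nothing requires it. Naming the combined estimate as the main one also settles which figure represents the product, even with the arms still on display.

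**Conclusion.** The point holds as a minor, optional improvement. The protocol contains no error or contradiction here, and the separate arm 2 and arm 3 estimates are valid. The loss is precision: each dose-1 interval is about 42% wider on the log scale than the combined one (1 / 0.70), and an event with a true rate of 1% has a 63.4% rather than 86.6% chance of being seen.

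This rests on three assumptions: Table 6's SDs apply to both arms, enrolment is close to 100 per arm, and the arms are exchangeable through Day 29, which randomisation and the shared schedule support. The SD 1.0 figures are the larger of the two planning cases.

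It is tempting to extend the combination to Day 57, because treatment is the same until then. The schedules do not support that: arm 2 has no Day 57 visit or sample, and its unsolicited event collection has ended by then. The combination should stop at Day 29.

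**What to change.** Add to sections 9.4.2, 9.4.4 and 9.4.6.2 wording such as: *For D1, D15 and D29 immunogenicity, and after dose 1 for solicited AEs through Day 8 and unsolicited AEs through Day 29, arms 2 and 3 will also be summarised as one combined Beta + Omicron group (n about 200). This is the main dose-1 estimate for that product. The separate arms are shown alongside. After Day 29 the arms are reported separately.*

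The cost is that wording and one extra table column, with no added subjects, visits or samples. There is one small downside. The trial is open label, so arm 3 subjects know that a second dose is coming, which might slightly affect how they report subjective symptoms. Keeping the separate columns leaves any such difference visible.
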